## **5.0 CLINICAL USE OF THE ANTI-ESTROGEN FULVESTRANT (FASLODEX®)**

Fulvestrant is the only endocrine therapy targeting the ER receptor that has been shown to have efficacy in tamoxifen resistant cancers in Phase 3 clinical trials. Two randomized trials have compared the efficacy of fulvestrant 250 mg IM with 1 mg oral anastrozole in postmenopausal women with advanced breast cancer whose disease had progressed after prior endocrine therapy. A combined analysis of these trials showed that fulvestrant was at least as effective as anastrozole (5.5 versus 4.1 months, respectively). Based on these trial

results, fulvestrant gained approval as an intramuscular injection of 250 mg once monthly dose level as a second-line treatment for postmenopausal women with hormone-sensitive breast cancer.

A subsequent randomized trial, CONFIRM, compared 250 mg with 500 mg monthly fulvestrant in 736 women and established a 500 mg dose to be superior in terms of Progression-free survival. At 18 months median follow-up PFS was 6.5 months in the 500 mg arm and 5.4 months in the 250 mg arm ( $p=0.006$ ). This study established 500 mg as the standard dose as described in the product labeling in the US and Europe, with a dose of 250 mg recommended for subjects with moderate hepatic impairment.

Neo-adjuvant use of fulvestrant in postmenopausal women with newly diagnosed invasive breast cancer was evaluated in the randomized “NEWEST” Phase 2 study, which randomized 211 subjects between 500 mg and 250 mg monthly intramuscular fulvestrant (with an extra dose on Day 14 of Month 1) for 16 weeks until surgery. Similar as in the study described in this protocol, change in Ki67 proliferation index 4 weeks after fulvestrant was the primary endpoint. By 4 weeks, the change from baseline in Ki67 labeling index was significantly different between the groups (-78.8 vs. -47.4%,  $p<0.0001$ ). Changes from baseline in ER expression were also significantly different between the groups ( $p<0.0002$ ), but changes in PgR expression were not. No safety concerns were identified.

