### **13.2 Sample Size and Statistical Analyses**

A total of 30 subjects who are undergoing mastectomy or lumpectomy will be included in this study: 6 will receive intramuscular, and 24 will receive intraductal fulvestrant. With respect to the sample size for the latter group with 24 subjects, it will be possible to detect an effect size of approximately 0.60 with 80% power and 0.69 with 90% power. Both of these are in the medium to large range according to Cohen's terminology and are based on the demonstration of a reduction in the Ki67 labeling index mean from baseline (diagnostic biopsy) to week 4 (surgically excised specimen) using a paired t-test. With these effect sizes and an anticipated 50% decline in the mean index, then the expectation would be a standard deviation in this reduction of about  $\pm 83.7\%$  for 80% power and  $\pm 72.3\%$  for 90% power.

The primary endpoint of this study is to assess safety and tolerability as measured by adverse events, subject pain assessment as well as signs of topical irritation seen on the excised specimen. In addition, the effect of the administration will be evaluated with respect to the change in Ki67 labeling index (primary efficacy endpoint) and changes in estrogen and progesterone receptor expression (secondary efficacy endpoints)

Descriptive statistics will be used to summarize the data (means/medians and standard deviations/interquartile ranges for quantitative data and proportions/percentages for categorical data such as adverse events), and numerically compare the groups with entry diagnoses of invasive ductal carcinoma and DCIS, respectively. In addition, the 6 study subjects who receive intramuscular fulvestrant will be qualitatively compared with the main study cohort of 24 subjects who receive intraductal fulvestrant.

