The primary analysis of the change in Ki67 labeling index will be compared between the two time points (baseline or time of diagnostic biopsy versus 4 weeks or time of the surgically excised specimen collection) using the paired t-test (assuming normality of the differences) or the Wilcoxon signed rank test if normality cannot be demonstrated or a transformation to normality using the Box-Cox family of power transformations cannot be used. A similar analysis will be employed to evaluate the secondary endpoint of changes in mean estrogen receptor and progesterone receptor expression. In addition, 95% confidence intervals for the mean difference for these variables between the two time points will be computed using the t-statistic or a rank statistic as required by the distribution of the study data.

The results for the efficacy endpoints will be compared in a descriptive fashion with those seen by Kuter et al (Kuter I, Gee JMW, Hegg R et al): Dose-dependent change in biomarkers during neoadjuvant endocrine therapy with fulvestrant: results from NEWEST, a randomized Phase II study. *Breast Cancer Res Treat* 133: 237-246, 2012.

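### Section 13.2 lets the data choose the Ki67 test and interval, and labels a rank-based interval as one for the mean difference

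*Combined protocol and SAP*

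**What the plan says.** Section 13.2 bases the sample size on the intraductal cohort ("6 will receive intramuscular, and 24 will receive intraductal fulvestrant") and a paired t-test of the change in Ki67 from diagnostic biopsy to surgical specimen. It states that "it will be possible to detect an effect size of approximately 0.60 with 80% power and 0.69 with 90% power", and ties this to "an anticipated 50% decline in the mean index" with a standard deviation of 83.7% for 80% power or 72.3% for 90% power.

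The analysis text of the same section uses the paired t-test if the differences are normal. Otherwise it gives this fallback: "Wilcoxon signed rank test if normality cannot be demonstrated or a transformation to normality using the Box-Cox family of power transformations cannot be used". ER and PgR expression are to be handled in the same way. The interval for all these variables is described thus: "confidence intervals for the mean difference for these variables between the two time points will be computed using the t-statistic or a rank statistic". The level is 95%, and the observed distribution decides which statistic is used.

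Three things are not stated: which normality test is used and at what level, which variable the Box-Cox transformation applies to, and whether the differences are in absolute Ki67 points or in percent.

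**The concern.** The interval has one stated target, the mean difference, and two possible constructions. Only the t construction aims at that target. Inverting the signed-rank test gives an interval for the pseudo-median, which is the median of all pairwise averages of the differences. For symmetric differences the two targets coincide. For skewed differences they do not, and skew is what sends the analysis down the rank route. The label is therefore most likely to be wrong in the cases where it matters.

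Because the switch has no stated test or threshold, two analysts following Section 13.2 could report different quantities under the same name. The result is also to be set beside a published neoadjuvant trial. Section 5.0 says of that trial that "the change from baseline in Ki67 labeling index was significantly different between the groups" and gives percent changes of -78.8 and -47.4, so it matters which quantity, on which scale, is being reported.

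The Box-Cox clause has a similar gap. The only variable whose normality the sentence mentions is the paired difference, and the one-parameter Box-Cox form requires positive data. Paired differences will normally have both signs.

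**Working it through.** **1. The plan's own figures reproduce.** Inputs from Section 13.2 are n = 24, a paired t-test and a 50% decline. The significance level is not stated. Two-sided 0.05 is assumed; it matches the 95% intervals and recovers the stated numbers. Power comes from the noncentral t distribution with 23 degrees of freedom and noncentrality d·√24.
- d = 0.60: noncentrality 2.94, power 0.804. d = 0.69: noncentrality 3.38, power 0.899.
- Exact detectable effects are 0.5972 (80% power) and 0.6911 (90% power). Then 50/0.5972 = 83.7 and 50/0.6911 ≈ 72.3, the stated SDs.

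The sample-size statement is sound for a paired t-test.

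**2. Do those figures suggest that the rank route will be used?** If the 50% and 83.7% are read as per-subject percent changes, a normal model puts Φ((-100 + 50)/83.7) = Φ(-0.597) = 27.5% of subjects below -100%. A non-negative index cannot fall that far, so on that scale normality is implausible at the plan's own SD. If the figures are instead read as fractions of the mean baseline index, the argument does not apply. The plan does not say which is meant.

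**3. How far apart are the two targets?** Both examples are assumed models.
- Absolute points: lognormal Ki67, log-SD 0.8 at both times, medians 15 and 7.5. Mean difference = -(15 - 7.5)·exp(0.8²/2) = -7.5 × 1.377 = -10.3. The pseudo-median is about -7.9.
- Percent change: lognormal ratio with mean 0.5 and SD 0.837. σ² = ln(1 + (0.837/0.5)²) = ln 3.80 = 1.34, so the median ratio is 0.5/√3.80 = 0.256. The mean change is -50% and the median change about -74%.

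**4. Coverage of the mean by the planned procedure.** These are simulations at n = 24 (4,000 trials per setting in the main runs), with Shapiro-Wilk at 0.05 and then a t or a signed-rank interval. The normality test and its level are assumptions. The Box-Cox step is left out because its target is unspecified.

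| Scale and assumed model | Planned interval covers the mean |
|---|---|
| Absolute points, mild skew | about 94% |
| Absolute points, lognormal, log-SD 0.8–1.0 | 76–89% |
| Percent change, lognormal ratio, SD 50% | about 78% |
| Percent change, lognormal ratio, SD 72.3% | about 69% |
| Percent change, lognormal ratio, SD 83.7% | about 61–62% |

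In the percent-change settings normality was rejected in 92%, 98% and 99% of trials, in the order of the rows, so the rank interval was almost always the one reported. A t interval fixed in advance covered the mean in about 90–94% of trials on absolute points and 84–90% on percent change. These figures move by a few points with the way the rank interval is built.

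**5. Type I error.** With no treatment effect and exchangeable readings, the two-stage rule rejected in 4.3–5.8% of trials, close to nominal.

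**The case against.** The strongest reply is that the damage depends on the scale and the skew. The interval is described for a difference in the index. On absolute points with mild skew, coverage is about 94%, and nothing in the documents shows that Ki67 will be strongly skewed. That stands as a limit on the size, but it does not repair the label: a rank interval is not an interval for the mean difference at any degree of skew.

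A second reply is that Section 13.0 promises a detailed SAP before database lock. It could settle these choices, but Section 13.0 gives the SAP the role of adding analyses that the protocol does not describe, and this rule is already described in Section 13.2. The study is open-label, so a time limit of database lock does not ensure that the choice is made before Ki67 results are known.

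Third, the study's primary endpoint is safety and tolerability. Ki67 leads only among the efficacy endpoints, which limits the consequence.

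A reader might also infer three stronger points that the documents do not support.
- *Box-Cox can never be run here.* The text does not say that it applies to the differences. It can run on positive raw Ki67 values, and the plan falls back on the signed-rank test where it cannot be used. The defect is an undefined step, not a broken analysis.
- *A log-ratio t-test would be clearly more powerful.* That holds under some multiplicative models, but no such model is in the documents. With normal Ki67 near the planned effect, the log ratio had 76–77% power against 79–81% for the planned rule. With 10% zero readings it had 60% (offset 1) or 22% (offset 0.01) against 89–90%. It also changes the estimand to a geometric mean ratio.
- *Pre-testing normality inflates the false-positive rate.* Step 5 of the working shows no material inflation.

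**Conclusion.** The point holds as one about an unfixed estimand and a mislabelled interval. Section 13.2 leaves the test, the scale and the target of the Ki67 interval open until the data are seen, and one of its two permitted intervals does not estimate the quantity named. The label error follows from the text alone. The size depends on assumptions: with lognormal data, 24 pairs and Shapiro-Wilk at 0.05, coverage of the mean is about 76–94% on absolute points and about 61–78% on percent change. If the differences are close to symmetric, the practical effect is small. The sample-size figures are not in question, and the case does not rest on type I error or on any power advantage of another method.

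**What to change.** In Section 13.2, before Ki67 data are seen:
1. State the scale of the change, absolute points or percent.
2. Name one primary test with its matching interval. The paired t-test and t interval are a natural choice because the sample size rests on them.
3. Keep the Wilcoxon signed-rank test as the pre-stated sensitivity analysis, with a Hodges-Lehmann interval labelled as estimating the pseudo-median.
4. Delete the switch on normality and the Box-Cox clause.
5. Apply the same labelling to ER and PgR.

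A log-ratio analysis reported as geometric mean percent change is an option, not a requirement. If it is chosen, the rule for zero readings must be fixed in advance, because the offset can decide the result.

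The cost is wording only. The downside is that, under strong skew, the pre-fixed t interval is itself below nominal (about 90–94% on absolute points and 84–90% on percent change in the same simulations). It does at least aim at the quantity that the plan names.

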### 13.3 Plasma Concentration Levels

The statistical analysis used for the pharmacokinetic (PK) population study may employ one or more of several advanced analysis packages including WinNonlin, Kinetica, Matlab, or R. For each subject, plasma level time curves will be assessed individually for the absorption rate and body compartment parameters. Both a one compartment and a two-compartment model will be considered. The literature values will be used for the initial conditions of the body compartment parameters, and a weighted nonlinear routine will be used for the parameter estimation. The optimal model will be chosen based on the Akaike Information Criterion (AIC).

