#### Equation 2. PK Model Selection Criterion

$$AIC = N * \ln(SSQ) + 2p$$

Here, N is the number of samples,  $\ln(SSQ)$  is the natural logarithm of the sum of the squared residues, and p is the number of model parameters. The model yielding the lowest AIC will be chosen.

Secondarily, standard parameters such as mass, body surface area, and body mass index will be assessed to determine if their inclusion will improve a joint parameter estimation using all subjects tested for a given agent dose. In the case that dosing for an agent was

terminated due to high AE, then such analyses will only be performed if sufficient subjects are available.

Standard PK parameters will then be calculated as appropriate to the modeling form (one or two compartmental model).

Differences between the absorption rate parameters and standard PK parameters will be assessed.

It is recognized that in some subjects, surgery may have already occurred before plasma  $C_{max}$  is reached.

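### Three informative plasma samples per subject cannot support the individual compartment fits in Section 13.3, and the AIC formula breaks down when a fit is exact

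*Combined protocol and SAP*

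**What the plan says.** Table 1 schedules four plasma samples per subject for both routes: pre-dose, 4.5 h, Day 7 and pre-surgery. Sections 9.5 and 9.6 place the last two at Day 5 to 9 and Day 14 to 21.

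Section 13.3 describes the analysis:
- Level of estimation: "For each subject, plasma level time curves will be assessed individually for the absorption rate and body compartment parameters".
- Candidate models: "Both a one compartment and a two-compartment model will be considered".
- Outside information: "The literature values will be used for the initial conditions of the body compartment parameters". No starting value is mentioned for the absorption rate.
- Model choice: Equation 2, AIC = N ln(SSQ) + 2p, where "N is the number of samples" and "The model yielding the lowest AIC will be chosen". The text does not say outright whether AIC is applied subject by subject.
- Pooling: as a second step, body-size covariates are tested in a "joint parameter estimation using all subjects tested for a given agent dose".
- Use of the results: "Differences between the absorption rate parameters and standard PK parameters will be assessed".

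The section opens by calling the work a population study ("The statistical analysis used for the pharmacokinetic (PK) population study may employ one or more of several advanced analysis packages"), and Section 13.0 names a population analysis, but neither describes a population model. Section 13.3 also accepts that some subjects may have surgery before Cmax. Under Section 9.1 the intraductal dose varies between subjects.

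**The concern.** The plan asks three observations to estimate three or five parameters in each subject, and then to choose between the two models. Secondary objective b (Section 6.2) is the comparison of intramuscular and intraductal PK, and Section 13.3 intends to compare absorption-rate and standard PK parameters. If those parameters come from the individual fits as described, the two-compartment values reflect partly where the solver started. The one-compartment values carry no check of fit and no internal error estimate. A difference between routes could then be an artefact of the fitting, and nothing in the output would show it.

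**Working it through.** The plan gives no figure of its own to reproduce here. Sample counts come from Table 1, footnote 3 of Table 2, and Sections 9.5 and 9.6. The documents list no model parameters and no PK values, so first-order absorption and all kinetic values below are assumptions (rates per day, dose 500 mg, concentration scale arbitrary).

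**1. Count.** Both models predict zero before dosing, so informative N = 4 − 1 = 3.
- One compartment (ka, k, V/F): 3 − 3 = 0 residual degrees of freedom.
- Two compartments (ka, k10, k12, k21, V/F): 3 − 5 = −2.
- One residual degree of freedom would take 4 and 6 post-dose samples respectively.

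**2. One compartment: the rate constants can be swapped.** C(t) = [D·ka / ((V/F)(ka − k))]·(e^(−kt) − e^(−ka·t)).
- (ka, k, V/F) = (0.15, 0.10, 30): multiplier 500 × 0.15 / (30 × 0.05) = 50.
- (0.10, 0.15, 20): multiplier 500 × 0.10 / (20 × −0.05) = −50, with the exponentials reversed.
- Both give 0.458, 7.332 and 4.905 at 4.5 h, Day 7 and Day 18.

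One subject's data cannot say which rate is absorption. AUC = D / (k × V/F) is unaffected: 500 / 3.0 = 166.7 in both cases.

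**3. Two compartments: not identifiable.** The sensitivity matrix is 3 × 5, so its rank cannot exceed 3 under any kinetics. Numerically it is 3 with the last sample at Day 14, 18 or 21. With assumed true values ka 0.12, CL/F 600, V1/F 1500, Q/F 600 and V2/F 4000, all 60 random starts reproduced the three concentrations. The fitted ka ran from 0.053 to 0.835 and CL/F from 154 to 755 L/day, on identical data.

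**4. AIC.** If SSQ = 0, ln(SSQ) is undefined. In practice the solver returns a tiny number set by its tolerance. The two-compartment model wins when N ln(SSQ1) + 6 > N ln(SSQ2) + 10, that is, when SSQ1/SSQ2 > exp(4/N). This is 3.79 for N = 3, or 2.72 if the pre-dose sample is counted (N = 4). Between two near-zero sums of squares, such a ratio carries no information about the model.

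**5. Does the choice track the truth?** Simulated per-subject fits: 100 profiles per setting, 10% or 25% noise, one or three starts. For a one-compartment truth, ka and CL/F are kept and V/F = V1/F + V2/F. Each cell gives one-compartment truth / two-compartment truth.

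| Assumed kinetics (ka, CL/F, V1/F, Q/F, V2/F) | Two-compartment chosen | One-compartment fit essentially exact |
|---|---|---|
| Peak about week 1 (0.12, 600, 1500, 600, 4000) | 2–21% / 0–9% | 31–54% / 88–100% |
| Peak after surgery (0.01, 100, 1500, 600, 4000) | 15–44% / 71–97% | 0–2% / 2–12% |
| Fast absorption, clear distribution phase (3, 300, 300, 300, 3000) | 0–7% / 100% | 93–100% / 0% |

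The choice fails to track in the first set, tracks partly in the second and tracks well in the third. A one-compartment curve is concave on the log scale, so it cannot follow a visible distribution phase. Even there, the chosen two-compartment model still has rank 3 of 5.

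**6. Does pooling alone cure it?** Pooling 24 intraductal subjects (24 × 3 = 72 samples) raises the two-compartment rank to 5. In a fit that ignores between-subject variation, however, every relative standard error exceeded 100% at 25% noise in all three sets (lowest 129%). Outside disposition values, or a simpler target, are still needed.

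**The case against.** The best defence is that the individual step is not the whole plan. Section 13.0 says a population analysis will be used and promises a detailed SAP before database lock. That is a real opportunity to repair the analysis. But the population model is not described, and the only pooled step in Section 13.3 is secondary, is for covariates, and is limited to a given dose. The sentence about additional analyses covers what the sections do not describe; the individual fits are described, and nothing says they will be replaced.

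A second defence is that literature values anchor the fit. If they were fixed and only ka estimated, each fit would be identifiable. Initial conditions, though, most naturally means starting values.

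A third is that the stakes are modest. That stands: the profile is described as abbreviated, the objective is secondary, and Section 13.2 compares the intramuscular subjects only qualitatively.

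Three stronger readings are tempting but not supported:
- A reader might infer that AIC never tracks the true structure, or that these data could never settle it. Step 5 shows that this depends on kinetics the documents do not give.
- A reader might infer that, if SSQ is summed over all subjects, the choice rests on whether p is counted as 3 v 5 or 90 v 150. In one simulated setting with 30% noise, one-compartment was picked in 22% v 100% of trials when true, and in 9% v 71% when two-compartment was true. At 10% noise the figures were 84% v 100%, and 77% under either count. The plan should state the count, but it does not always decide the result.
- A reader might infer that exposure is lost as well. AUC survives the swap in step 2. In a noise-free two-compartment check with correct body starts, AUC stayed at 52.9–58.5 (true 55.6) across five ka starts. With body starts off by a factor of 1.25, the upper end was 65.9 or 101.0 depending on the solver set-up, so the drift is real but its size is not fixed.

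**Conclusion.** The point holds. Under first-order absorption, the sample count, the rank limit, the ka/k swap and the AIC algebra are independent of any PK values. As written, Section 13.3 yields one-compartment estimates that are saturated and ambiguous about absorption, two-compartment estimates that are not identifiable, and a selection rule that is unreliable and undefined at an exact fit. How often fits are exact, and how often the choice is right, vary with assumed kinetics and noise. Only secondary objective b is affected; the safety endpoint, the Ki67 analysis and the dose-limiting toxicity rules do not use these parameters. It should be fixed before database lock.

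**What to change.** Revise Section 13.3 and carry the detail into the SAP:

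1. Make the main route comparison a table of concentrations by route at 4.5 h, Day 7 and pre-surgery, as observed and divided by the actual dose, with actual sampling times. This needs no outside values.
2. Remove the per-subject estimation of all compartment parameters and the per-subject AIC choice. Base any model parameters on the pooled population analysis already named in Section 13.0. Use each subject's actual dose and times as inputs, replacing the restriction to a given dose.
3. Before database lock, name in the SAP the structural model and any disposition rate constants fixed at sourced values. Estimate V/F, absorption rate by route and relative bioavailability. Run the other structure and a stated range of fixed values as sensitivity analyses. Include between-subject variability in absorption only if the data support it. Report route results descriptively with intervals.

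Fixing rate constants in a pooled mixed-effects model is one reasonable option, not the only one. The cost is wording and code, with no new samples. The downsides are reliance on outside constants and low precision with the 6 intramuscular subjects of Section 13.2. In a simulation (assumed kinetics, 30% between-subject and residual variation, intraductal doses 200–500 mg) with correct one-compartment constants, relative bioavailability had median 0.99 (95% range 0.69–1.49; true 1.0). A 25% error in the fixed elimination rate moved the median to 0.95 or 1.04 with V/F estimated, but to 0.75 or 1.29 with V/F fixed too; hence V/F should be estimated. The between-subject SD of absorption was weakly informed (true 0.30, 95% range 0.00–0.52).
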